## **Study Design and Endpoints**

This is a randomized, double-blind, placebo-controlled, design. We propose the administration of an investigational drug in patients with high predicted short-term mortality secondary to COVID-19 disease. 30 Patients will be randomly assigned in a 1:1 ratio to two study arms that will receive clazakizumab at a dose of 25 mg or placebo.

Primary Study Endpoints

The primary endpoint is patient safety assessed by serious adverse events associated with clazakizumab or placebo.

Secondary Study Endpoints

The secondary endpoints are: incidence of intubation, time to extubation, length of ICU stay, trend in C-reactive protein, severity of AKI, need for RRT, duration of RRT, and patient survival at 28 and 60 days.

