The PI will record all reportable events related to the Infusion of the Investigational Product with start dates occurring any time after informed consent is obtained until 7 (for non-serious AEs and SAEs) after the last day of study participation. At each study visit, the investigator will inquire about the occurrence of AE/SAEs since the last visit. Events will be followed for outcome information until resolution or stabilization. All unresolved adverse events should be followed by the investigator until the events are resolved, the subject is lost to follow-up, or the adverse event is otherwise explained. At the last scheduled visit, the investigator should instruct each subject to report any subsequent event(s) that the subject, or the subject's personal physician, believes might reasonably be related to participation in this study. The investigator should notify Vitaeris of any death or adverse event occurring at any time after a subject has discontinued or terminated study participation that may reasonably be related to this study. Vitaeris should also be notified if the investigator should become aware of the development of cancer or of a congenital anomaly in a subsequently conceived offspring of a subject that has participated in this study.

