## Statistical and Analytical Plans (SAP)

Descriptive statistics for the safety endpoints will be used. With 10 patients, the 95% confidence interval (CI) around the rate of SAEs will be no more than 0.62 units wide. With 20 patients (combining the low dose and high-dose groups), the 95% CI will be no more than 0.46 units wide. Regarding the secondary outcome of patient survival, too little is known about the expected clinical behavior of these patients to make meaningful projections about expected changes in mortality given drug efficacy. Data will be analyzed across three sites: NYU, where this protocol originated; Columbia/NYP; and Johns Hopkins.

The first 80 patients at NYU were enrolled in the three-arm study using a 1:1:1 ratio. Following the DSMB's recommendation, additional NYU patients (expected to be 10) will be randomized in a 1:1 ratio to placebo or 25 mg clazakizumab. Columbia/NYP and Johns Hopkins will each enroll 30 patients in a 1:1 randomization ratio, with 15 patients each on clazakizumab 25mg and placebo. At these other sites, with 15 patients, the 95% confidence interval (CI) around the rate of SAEs will be no more than 0.52 units wide. The total planned enrollment of 150 subjects across these three sites will considerably increase the power to detect treatment effects. The table below summarizes approximate power for the projected sample size in the placebo and 25 mg clazakizumab groups (N=60 in each arm) to detect various reductions in mortality from the expected 50% rate in the placebo group, for various levels of Type I error (alpha) assuming use of a two-sided test. For example, we have approximately 82% power

to detect a reduction in the mortality rate of 50%, from 0.5 in the placebo group to 0.25 in the treated group, assuming 60 patients per group, at the usual Type I error rate of 0.05.

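### The only adverse-event recording rule is limited to infusion-related events, and the plan does not settle whether the primary safety endpoint counts related SAEs or all SAEs

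*Combined protocol and SAP*

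**What the plan says.** Objectives and Purpose makes safety the primary objective. Under Study Design and Endpoints: "The primary endpoint is patient safety assessed by serious adverse events associated with clazakizumab or placebo". Neither section explains what an association with drug or placebo means.

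The adverse-event paragraph that closes Study Procedures, after the schedule of events, gives the recording rule: "The PI will record all reportable events related to the Infusion of the Investigational Product". It does not define a reportable event, and no rule for judging causality is given.

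The rest of the same paragraph is wider. On enquiry: "At each study visit, the investigator will inquire about the occurrence of AE/SAEs since the last visit". On follow-up: "All unresolved adverse events should be followed by the investigator until the events are resolved". The manufacturer is to be told of events arising "after a subject has discontinued or terminated study participation that may reasonably be related to this study", a test that on its words is broader than the in-study rule. Participant Withdrawal or Termination and the day 28 and day 60 entries in the schedule also ask about interim AEs and SAEs, with no mention of relatedness.

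The SAP plans descriptive statistics and sizes the safety estimate on an unqualified SAE rate: "with 15 patients, the 95% confidence interval (CI) around the rate of SAEs will be no more than 0.52 units wide".

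**The concern.** A rate of SAEs related to the infusion and a rate of all SAEs are different quantities. The plan supports both readings and does not say which will be reported as the primary result.

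The narrow reading discards information that the design was built to provide. With randomisation and a blinded placebo arm, SAEs of any cause can be compared by arm without anyone having to decide, case by case, whether the drug was responsible. If recording depends on that judgement, an event put down to COVID-19 never enters the safety data and may not be recoverable later. An all-cause record, by contrast, can always be filtered by relatedness at analysis.

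The exposed events are serious ones with no other route into the dataset. Death, intubation, AKI and RRT are collected as secondary outcomes whatever their cause. Serious infection is not. The SAP expects 50% mortality on placebo, so serious events attributable to the disease may be common.

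**Working it through.** **1. Which reading does each place support?**

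| Place | Topic | Limited to related events? |
|---|---|---|
| Study Procedures, adverse-event paragraph | What is recorded | Yes, related to the infusion |
| Same paragraph | Enquiry at each visit | No |
| Same paragraph | Follow-up of unresolved events | No |
| Same paragraph | Events after participation | Yes, but related to the study, which is wider |
| Participant Withdrawal or Termination; schedule, days 28 and 60 | Interim AEs/SAEs | No |
| Study Design and Endpoints | Primary endpoint | Ambiguous: attributed to the product, or occurring on either arm |
| SAP | SAE rate | No |

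Only the first row governs what is written down, and it is the narrowest.

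**2. Can the SAP's figures decide the question?** I reproduced the stated interval widths as the maximum width of the exact (Clopper-Pearson) 95% interval over all possible event counts.

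| n | Stated | Reproduced |
|---|---|---|
| 10 | 0.62 | 0.626 |
| 15 | 0.52 | 0.521 |
| 20 | 0.46 | 0.456 |

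All agree within 0.01. They are worst cases over every possible rate, so they are the same for related and for all SAEs. They do not show which is meant, and none changes.

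**3. How different could the two rates be at this site?** The documents give no SAE rate, so these counts are assumed. One related SAE patient in 15 gives an exact 95% interval of 0.002 to 0.319. Ten patients with any SAE in 15 gives 0.384 to 0.882. Both fit the plan as written.

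**4. What would filtering at this site alone do to the pooled comparison?**

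- From the documents: "N=60 in each arm" in the SAP; 15 per arm at this site (Randomization). That leaves 60 - 15 = 45 per arm elsewhere.
- Assumed: serious infection in 20% (placebo) v 35% (drug) of patients; the other sites record everything; a share s of events is recorded at this site, the same in both arms.
- Expected counts: a = (45 + 15s) × 0.20 and b = (45 + 15s) × 0.35. The factor (45 + 15s) cancels, so the ratio b/a stays at 1.75.
- Approximate 95% interval: exp(ln 1.75 ± 1.96 × √(1/a - 1/60 + 1/b - 1/60)).

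| Share s | a v b | Recorded rate, placebo v drug | Interval for the ratio |
|---|---|---|---|
| 1 | 12 v 21 | 20% v 35% | 0.95-3.23 |
| 0.8 | 11.4 v 19.95 | 19% v 33% | 0.93-3.30 |
| 0.5 | 10.5 v 18.4 | 17.5% v 31% | 0.90-3.41 |
| 0.2 | 9.6 v 16.8 | 16% v 28% | 0.86-3.55 |

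At half those risks (10% v 17.5%), the interval is 0.69-4.47 with all recorded and 0.60-5.07 at s = 0.2. In both cases the rates are understated, the ratio is unchanged and the interval widens modestly.

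**The case against.** The strongest reply is that the literal reading defeats itself. Recording starts at informed consent, and screening may begin five days before treatment, yet an event before the infusion cannot be related to it. The same sentence describes its window as "until 7 (for non-serious AEs and SAEs) after the last day of study participation", again with no relatedness limit, and everything that follows in the paragraph is unrestricted. The clause may simply be loose wording. That is a fair account of the likely intent, and it stands. It does not remove the problem, because asking about events is not the same as recording them, and this clause is the one that site staff would follow when deciding what to enter.

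It is also fair that the SAP specifies only descriptive safety statistics, so the ratio intervals above measure precision in a comparison that the plan does not itself specify. In addition, the Rationale presents the treatment as immunosuppressive, so blinded investigators may be reluctant to call serious infections unrelated. Both points limit the size. Neither says which SAEs the primary endpoint counts.

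A reader might go further and infer that the recording window is also defective, since no unit follows the 7. That is not supported: the unit may have been lost in text extraction, and a start at consent with an end tied to 60-day participation is not contradictory.

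**Conclusion.** The point holds and should be fixed. The scope of the primary endpoint is not settled, and the one operative recording rule points to the narrower and less useful version. Taken literally, it understates SAE rates and gives up the all-cause comparison by arm. No stated number is wrong.

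The size is unknown. The documents give neither an infection risk nor an attribution share, and fuller adverse-event rules may exist in documents not supplied. On the assumptions shown, filtering at this site alone has a small effect on pooled precision.

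Two stronger conclusions might be inferred, and the documents support neither. One is that the pooled safety comparison is badly degraded. That requires all three sites to apply this clause. The SAP says the protocol originated at NYU, so the wording may be shared, but the other sites' rules are not shown and each site's conduct is overseen by its own IRB. The other is that the comparison is biased or a signal erased. If the same filter acts in both blinded arms, the rates and their difference shrink while the ratio is unchanged.

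**What to change.** - **Study Procedures, adverse-event paragraph:** require all SAEs to be recorded regardless of their relationship to the investigational product, with the blinded relatedness judgement kept as a separate variable.
- **Study Design and Endpoints:** define the primary endpoint as SAEs of any cause by arm, reported with the 95% confidence intervals that the SAP already plans. Keep related SAEs as a secondary tabulation.

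The change is confined to SAEs because the primary endpoint is. Recording every non-serious event regardless of cause would be a much larger burden in these patients and is not needed here.

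The cost is two edited sentences and more SAE entries in a very ill population, many of them due to COVID-19. AEs and SAEs are already asked about at each visit and at days 28 and 60, so the added work is mainly data entry.

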## Statistical and Analytical Plans (SAP)

Descriptive statistics for the safety endpoints will be used. With 10 patients, the 95% confidence interval (CI) around the rate of SAEs will be no more than 0.62 units wide. With 20 patients (combining the low dose and high-dose groups), the 95% CI will be no more than 0.46 units wide. Regarding the secondary outcome of patient survival, too little is known about the expected clinical behavior of these patients to make meaningful projections about expected changes in mortality given drug efficacy. Data will be analyzed across three sites: NYU, where this protocol originated; Columbia/NYP; and Johns Hopkins.

The first 80 patients at NYU were enrolled in the three-arm study using a 1:1:1 ratio. Following the DSMB's recommendation, additional NYU patients (expected to be 10) will be randomized in a 1:1 ratio to placebo or 25 mg clazakizumab. Columbia/NYP and Johns Hopkins will each enroll 30 patients in a 1:1 randomization ratio, with 15 patients each on clazakizumab 25mg and placebo. At these other sites, with 15 patients, the 95% confidence interval (CI) around the rate of SAEs will be no more than 0.52 units wide. The total planned enrollment of 150 subjects across these three sites will considerably increase the power to detect treatment effects. The table below summarizes approximate power for the projected sample size in the placebo and 25 mg clazakizumab groups (N=60 in each arm) to detect various reductions in mortality from the expected 50% rate in the placebo group, for various levels of Type I error (alpha) assuming use of a two-sided test. For example, we have approximately 82% power

to detect a reduction in the mortality rate of 50%, from 0.5 in the placebo group to 0.25 in the treated group, assuming 60 patients per group, at the usual Type I error rate of 0.05.

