## **Objectives and Purpose**

## Primary Objective

The primary objective is to assess the safety of clazakizumab treatment in COVID-19 infected patients with respiratory failure due to hyperinflammation related to cytokine storm. Secondary Objectives

The secondary objectives are to assess efficacy by evaluating the incidence and duration of mechanical ventilation, the length of ICU stay, severity and duration of acute kidney injury (AKI) and patient survival in patients who receive IP at two different doses versus placebo.

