## **Strategies for Recruitment and Retention**

The patients enrolled will be identified by the members of the Columbia University Irving Medical Center / New York Presbyterian Hospital (CUIMC/NYPH) COVID-19 inpatient team who have identified the potential subject as critically ill and failing all available medical and supportive therapies. Patient recruitment will begin by direct communication between the COVID-19 inpatient team and the study team. An individual involved in the patient's care must determine and document that the patient or their surrogate (if the patient lacks capacity) has agreed to discuss the study with the researchers. Duration of Study Participation

The entire duration of study participation is 60 days. Study specific laboratory tests will be performed within the first 14 days of study initiation. Beyond 14 days, all data collected will be that which is acquired for purposes of clinical care. Patients will be followed for the survival endpoint for 60 days. Total Number of Participants and Sites

The CUIMC/NYP inpatient hospital site is expected to enroll up to30 patients across the 2 arms. NYU will serve as the central data managing site, and will analyze data from patients enrolled at NYU, Columbia, and Johns Hopkins. Total enrollment is expected to be 150 patients across three sites. Expected contribution of patients will be: NYU Langone (New York, NY): 90 total patients (80 already randomized 1:1:1 and 10 to be randomized 1:1 for high-dose clazakizumab 25mg vs placebo) Johns Hopkins Medicine (Baltimore, MD): 30 patients to be randomized 1:1 for high-dose clazakizumab 25mg vs placebo New York-Presbyterian/Columbia University (New York, NY): 30 patients to be randomized 1:1 for high dose clazakizumab 25mg vs placebo Columbia and Johns Hopkins will contribute de-identified data to the central dataset but the conduct of the trial at each site will be overseen by the local IRB the respective sites.

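### Mortality is pooled over four separate randomisations with no stated stratification, and the low-dose wording does not fit the two-arm design (minor)

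*Combined protocol and SAP*

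**What the plan says.** **Streams.** The Statistical and Analytical Plans section states: "The first 80 patients at NYU were enrolled in the three-arm study using a 1:1:1 ratio". After a DSMB recommendation, about 10 further NYU patients are split 1:1 between placebo and 25 mg. Columbia/NYP and Johns Hopkins each add 30 patients at 1:1. Strategies for Recruitment and Retention agrees, giving NYU as "80 already randomized 1:1:1 and 10 to be randomized 1:1 for high-dose clazakizumab 25mg vs placebo". It makes NYU the site that manages and analyses the data, and says "Columbia and Johns Hopkins will contribute de-identified data to the central dataset".

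**Analysis.** The commitment is "Data will be analyzed across three sites: NYU, where this protocol originated; Columbia/NYP; and Johns Hopkins". Power is given for the "projected sample size in the placebo and 25 mg clazakizumab groups (N=60 in each arm"), using a two-sided test. No test or model for mortality is named, and no site or stage term is mentioned. The Randomization section specifies stratified blocks for the 30 Columbia patients but names no stratification factors.

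**Doses.** The secondary objectives include "patient survival in patients who receive IP at two different doses versus placebo". The SAP also says: "With 20 patients (combining the low dose and high-dose groups), the 95% CI will be no more than 0.46 units wide". Study Design and Endpoints has only two arms, one of them placebo: "30 Patients will be randomly assigned in a 1:1 ratio to two study arms that will receive clazakizumab at a dose of 25 mg". Randomization and Study Procedures say the same.

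**The concern.** The four streams were randomised separately, at different hospitals or in different periods, and one of them had a third arm. Placebo mortality may well differ between them. An analysis that follows the randomisation compares arms within each stream and then combines the results. The plan does not say whether this will be done, which leaves the choice to the analyst for the only comparison that has a power calculation.

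The dose wording makes this matter more. If both doses were put together against placebo, the active-to-placebo ratio would be about 2:1 in the first NYU stream and 1:1 elsewhere. Differences in mortality between streams would then be mixed with the treatment effect. The plan does not say whether any low-dose or combined-dose comparison of survival will be made, or with which placebo patients.

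**Working it through.** **Inputs from the documents.** Stream sizes and ratios: 80 (1:1:1), about 10 (1:1), 30 (1:1), 30 (1:1). Mortality 0.50 versus 0.25, 60 per arm, two-sided 0.05, stated power about 82%. The documents give no mortality by site or stage, so every stream-specific rate below is an assumption.

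**1. Arm sizes.** Placebo and 25 mg each have 80/3 + 5 + 15 + 15 = 61.7, consistent with the plan's 60.

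**2. The stated power.** Two-proportion test, pooled variance under the null, mean rate 0.375.
- SE under the null = √(2 × 0.375 × 0.625 / 60) = 0.0884
- SE under the alternative = √((0.25 + 0.1875) / 60) = 0.0854
- Power = Φ((0.25 − 1.96 × 0.0884) / 0.0854) = Φ(0.899) = 81.6%

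The plan's figure is reproduced without any site or stage term.

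**3. Does pooling bias 25 mg versus placebo?** In whole patients each arm has 27, 5, 15 and 15 from the four streams. Both arms therefore carry the same stream weights (27/62, 5/62, 15/62, 15/62). With no drug effect the expected pooled difference is zero, whatever the mortality in each stream.

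**4. What stratifying gains for 25 mg versus placebo.** Simulation, 1,000,000 trials per scenario, common odds ratio 1/3 (which takes 0.50 to 0.25), pooled z-test against CMH without continuity correction:

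| Assumed placebo mortality by stream | Unstratified power | CMH power |
|---|---|---|
| 50% everywhere | 83.4% | 83.3% |
| 50% first NYU stream, 45% elsewhere | 81.6% | 81.6% |
| 50%, 40% elsewhere | 79.6% | 79.7% |
| 50%, 35% elsewhere | 77.2% | 77.8% |
| 50%, 30% elsewhere | 74.3% | 75.4% |
| 70 / 50 / 30 / 30% (extreme) | 73.8% | 77.6% |

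**5. Both doses combined against placebo, no drug effect.** The active group has 54 + 5 + 15 + 15 = 89 patients and placebo has 62. The first NYU stream makes up 54/89 = 0.607 of the active group and 27/62 = 0.435 of placebo. If its mortality differs from the rest by d, the false difference is d × (0.607 − 0.435) = 0.171d.
- 50% then 40%: 0.171 × 10 = 1.7 points; unstratified type I error 5.6%
- 50% then 30%: 0.171 × 20 = 3.4 points; 6.8%
- 70 / 50 / 30 / 30%: (37.8 + 2.5 + 9)/89 − (18.9 + 2.5 + 9)/62 = 0.554 − 0.490 = 6.4 points; about 10%

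CMH stays at about 5% in all three. When the first stream has the higher mortality the false difference goes against the drug; when it has the lower mortality it favours the drug.

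**6. Low dose against concurrent placebo.** With 80/3 = 26.7 per arm and 0.50 versus 0.25, the formula in step 2 gives SEs of 0.1326 and 0.1281, and power = Φ((0.25 − 1.96 × 0.1326) / 0.1281) = Φ(−0.077) = 47%. At 50% mortality the 95% CI half-width is 1.96 × √(2 × 0.25 / 26.7) = 0.268, about 27 points.

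**The case against.** The strongest reply is that the plan contains no statistical error here. It is silent on stratification and does not exclude it. The match at 81.6% does not show that an unstratified analysis is intended: it is a planning formula, and step 4 shows that stratified and unstratified power are almost equal at 50% mortality. The 4-point gain needs a mortality pattern for which the documents offer no support. Survival is a secondary endpoint and the primary safety endpoint is descriptive. All of this stands, and it is why the point is minor.

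The two-dose objective can also be read as describing the central dataset, which includes NYU patients randomised to the low dose. That is plausible, but the text does not say so. The combined-dose sentence concerns only the precision of a safety rate, so the calculation in step 5 is conditional on the same grouping being used for survival.

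Three stronger readings are tempting and are not supported.
- A reader might infer that pooling inflates false positives for 25 mg versus placebo. The unstratified test does have 5.9% error at 62 per arm, but with 50% mortality everywhere, where there is nothing to stratify for. Exact enumeration gives 4.9% at 57 per arm, 5.5% at 60 and 4.5% at 64. This is the discreteness of the test.
- A reader might infer that low-dose patients will be compared with every placebo patient, concurrent or not. No section proposes that.
- A reader might expect stratification to deal with the choice of dose after the first NYU stream. A stage term would not do that, and the documents do not give the basis of the DSMB recommendation.

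**Conclusion.** The point holds as a minor one. The 82% power is correct, and 25 mg versus placebo is unbiased with or without strata. Stratifying that comparison by stream is an essentially free improvement worth about 0 to 1 point of power under assumed moderate differences between streams, and about 4 points in the assumed extreme case. No protection against excess false positives is claimed for it.

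The stronger reason to write the strata down is the unsettled dose wording. If both doses were combined against placebo, an unstratified test could show a false difference of about 2 to 6 points, with a type I error of about 6% to 10%, under assumed stream differences of 10 to 40 points. The size and direction in this trial are unknown, because no mortality by site or stage is given.

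The conflict between the two-dose objective and the two-arm design is a plain inconsistency in the text and rests on no assumption.

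**What to change.** - State that mortality at days 28 and 60 for 25 mg versus placebo will be analysed with a CMH test over four strata: NYU first stage, NYU second stage, Columbia/NYP and Johns Hopkins. If both doses are ever combined against placebo, use the same strata.
- Reconcile the secondary objective and the SAP's combined-dose sentence with the two-arm design in Study Design and Endpoints, Randomization and Study Procedures. Say whether any low-dose comparison will be made.
- If one is kept, restrict it to the 80 concurrently randomised NYU patients and label it descriptive, quoting the power of about 47% for 0.50 versus 0.25.

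**Cost.** Wording only. Site and stage are known for every patient, so no new data or patients are needed, and the power for 25 mg versus placebo is essentially unchanged or slightly better. NYU analyses the pooled data, so the wording has to be agreed there; a change in this document alone may not bind the pooled analysis.

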## **Study Procedures**

This is a randomized, double-blind, placebo-controlled, adaptive seamless Phase II/III design (ASD). The investigators propose the administration of an investigational drug in patients with high predicted short-term mortality secondary to COVID-19 disease. Patients will be enrolled and randomly assigned in a 1:1 ratio to two study arms that will receive clazakizumab at a dose of 25 mg or placebo. Experimental: Clazakizumab Group

The first dose will be administered as soon as possible after the patient is enrolled and randomized into the Clazakizumab 25 mg arm. The route of administration will be intravenous. Each dose will be administered as an infusion that is run over 30 minutes. Serum C-reactive protein (CRP) will be evaluated at baseline and on days 1 and 2 following clazakizumab administration. If the CRP does not decrease by 50% within 36-48 hours after the first dose, a second dose of 25 mg clazakizumab will be given no later than day 3.

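### Does pooling patients from before and after the DSMB-recommended change of arms undermine the 25 mg versus placebo mortality comparison?

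*Combined protocol and SAP*

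**What the plan says.** The combined protocol and SAP describes two enrolment stages. Under Strategies for Recruitment and Retention, NYU contributes 90 patients, "80 already randomized 1:1:1 and 10 to be randomized 1:1 for high-dose clazakizumab 25mg vs placebo". Columbia/NYP and Johns Hopkins contribute 30 each, 1:1, for a total of 150. The SAP section gives the reason for the change in one sentence: "Following the DSMB's recommendation, additional NYU patients (expected to be 10) will be randomized in a 1:1 ratio to placebo or 25 mg clazakizumab".

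On analysis, the SAP section says: "Data will be analyzed across three sites: NYU, where this protocol originated; Columbia/NYP; and Johns Hopkins". The recruitment section names who does it: "NYU will serve as the central data managing site, and will analyze data from patients enrolled at NYU, Columbia, and Johns Hopkins". The SAP's worked example gives about 82% power for mortality of 0.50 versus 0.25, two-sided, "assuming 60 patients per group, at the usual Type I error rate of 0.05".

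The Study Procedures section labels the design adaptive and seamless (phase II/III), and the Blinding section leaves interim analyses to an independent monitor. The secondary objectives still mention "patient survival in patients who receive IP at two different doses versus placebo", while the power statement concerns 25 mg and placebo only. Nowhere does the document state the basis of the DSMB recommendation, a selection rule, or a method for combining the stages.

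The primary endpoint is serious adverse events, analysed descriptively. Survival is one of several secondary endpoints, and the SAP itself says too little is known to project mortality changes meaningfully.

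**The concern.** When an arm is dropped after a look at comparative data, and patients from before the look are kept in the final comparison, the retained comparison may have been selected partly by chance. A plain pooled test then need not hold its nominal error in each tail, and the estimated difference can be biased. Here about four in ten patients in each compared arm predate the change. The document calls the design adaptive, yet quotes power for a single-stage test "at the usual Type I error rate of 0.05" without mentioning an adjustment.

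At stake is how far a reader could trust a mortality benefit (or a null result) from the pooled data. The worry is not confined to a DSMB decision based on deaths. A decision based on serious adverse events, intubation or renal replacement would carry over to mortality in so far as those outcomes go with death. It would also affect pooled event rates for the primary safety endpoint, although those are reported without a test.

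**Working it through.** **Inputs from the document.** 80 patients 1:1:1; then 10 + 30 + 30 patients 1:1; 60 per arm for power; mortality 0.50 versus 0.25; two-sided alpha 0.05.

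**Is pooling implied?**
- First stage per arm: 80/3 = 26.7.
- Second stage per arm: 5 + 15 + 15 = 35.
- Sum: 61.7, which the plan rounds to 60.

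Thirty-five alone cannot give 60, so first-stage patients are counted. Taking 25 + 35 = 60, the first-stage share is 25/60 = 42%.

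**The plan's own figure.** For the two-proportion z-test, power = Φ{[Δ − 1.96·√(2p̄(1−p̄)/n)] / √([p₁(1−p₁)+p₂(1−p₂)]/n)}, with Δ = 0.25 and p̄ = 0.375.
- n = 60: (0.25 − 1.96 × 0.0884)/0.0854 = 0.90, giving 0.816. Exact binomial power of the same test is 0.818. The 82% is reproduced.
- n = 35 (second stage only): (0.25 − 1.96 × 0.1157)/0.1118 = 0.21, giving 0.582. Exact power is 0.589.

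**Does stage confound the comparison?** No. Placebo and 25 mg are allocated equally in both stages, apart from the small imbalance because 80 is not divisible by three. A shift in mortality over time or between sites therefore affects both arms alike. The only route to bias is selection.

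**How large could selection bias be?** The document gives no rule, so the rules below are assumptions. The null is 50% mortality in every arm, with 25 + 35 per arm and the uncorrected pooled z-test. Results come from exact binomial enumeration, conditional on the rule having led to 25 mg versus placebo. Positive bias favours the drug.

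| Assumed basis of the change | Benefit tail | Harm tail | Bias (points) |
|---|---|---|---|
| Unrelated to outcome | 2.7% | 2.7% | 0 |
| Dose with lower mortality kept | 4.3% | 1.2% | +2.3 |
| Low dose dropped: worse than placebo | 1.1% | 4.6% | −2.6 |
| Low dose dropped: worst of three arms | 1.7% | 1.7% | 0 |
| 25 mg required to beat both other arms | 7.1% | 0.1% | +5.9 |

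The null standard error at 60 per arm is √(0.5/60) = 9.1 points. The non-zero biases are 2.3/9.1 = 0.3, 2.6/9.1 = 0.3 and 5.9/9.1 = 0.6 of it. Under the second rule, total two-sided error stays at 5.5%, the same as with no selection; only the split between tails moves.

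**If the DSMB acted on adverse events instead.** Assume a patient-level correlation of 0.5 between serious adverse events and death (normal approximation). Keeping the dose with fewer events gives a bias of about +1.2 points; requiring 25 mg to have the fewest of three arms gives about +2.6. At a correlation of 0.9 these become +2.1 and +4.8. These biases are smaller than under the matching mortality rules, but not zero.

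**What would a safeguard cost?** Leading with the second stage alone cuts power for 0.50 versus 0.25 from 82% to 58%. For 80% power, treated mortality must then fall to about 0.19 instead of 0.25.

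**The case for a change.** The strongest case for a change is that the gap is real and cheap to close. Pooling across the change is required by the stated sample size. Mortality is the only endpoint given a power calculation. The DSMB and the originating site presumably know what the recommendation rested on. A few sentences naming the pooled test, and placing the 35-per-arm result beside it, would need no extra patients and cost no power. Written before unblinding, they would also prevent a choice between pooled and second-stage results after both are known.

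The facts in that case stand, and so does the value of showing both results. What does not follow is that the plan is wrong:

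- **No stated method is faulty.** The document prescribes no mortality test, so there is no rule to replace. The 82% is right for what it describes.
- **The direction is unknown.** Of the five assumed rules, two give no bias, one works against the drug and two favour it. An adjustment could as easily be needless as helpful.
- **The detail may be elsewhere.** The analysis belongs to NYU, where the trial began. This contributing-site document may simply not repeat that site's plan, though it gives no reference to one for these points.
- **Silence has a reason.** Investigators and sponsor are meant to remain blinded. Writing the basis of a DSMB recommendation into a site document could disclose interim results.
- **The objectives wording is not a clear contradiction.** The dataset to be analysed includes the first-stage low-dose patients, so mention of two doses can describe it.

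**Conclusion.** No change to the plan follows. The 25 mg versus placebo mortality comparison does pool about 25 to 27 first-stage patients per arm with 35 randomized after the change, and this document gives neither the type of data behind the change nor the combination method. That is a minor reporting gap, not an error. The stated power is reproduced (81.6% by formula), allocation between the two compared arms is equal in both stages, and a pooled two-arm comparison is the natural default. The second-stage-only result can be produced from the same data without any amendment.

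If the change did not use unblinded comparative outcome data, pooling is unbiased. If it did, bias under the assumed rules lies between −2.6 and +5.9 points, at most about 0.6 of a standard error, and its sign cannot be told from the document. Making the second stage the lead analysis would give up 82 − 58 = 24 points of power to guard against that possibility, which is at best a debatable trade.

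Two limits apply. The condition for unbiased pooling is independence from any outcome associated with death, not from mortality alone. Nor can it be said that the primary safety endpoint is untouched: a recommendation based on adverse events could bias pooled event rates, although their analysis is descriptive and involves no test. The figures rest on 50% mortality, 25 + 35 per arm and hypothetical rules, none of which the document confirms as the DSMB's basis.
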